7.C. N-Acetylcysteine: NAC is likely safe for most adults, when used as a prescription medication. It can cause gastrointestinal side effects such as nausea or abdominal pain, as well as headache and hypersensitivity reactions. Based on the mechanism of anti-oxidant effects of NAC, no potential drug interactions would be anticipated in PD patients on an MAO inhibitor.

We anticipate that gastrointestinal side effects will be dose-related. If these symptoms occur at the initial dose, they will be considered to be expected non-serious adverse events and reported as such, and the dose will be decreased by one-half. If the symptoms occur at the lower dose, then the NAC will be stopped, the patient will be withdrawn from the study, and the patient will be observed as an inpatient until the symptoms resolve.

Rarely, NAC can cause rashes, fever, headache, drowsiness, low blood pressure, or liver problems. If a patient experiences these symptoms or signs or others that in the opinion of the Principal Investigator are the result of NAC, the patient will be withdrawn from the study.

7.D. Radiation (fluoroscopy): This research study involves exposure to radiation from fluoroscopy if technical difficulty is anticipated or experienced with the lumbar puncture. This radiation exposure is not required for medical care and is for research purposes only. The estimated Effective Dose, **0.05 rem** (2 fluoroscopy procedures), is below the guideline of 5 rem per year allowed for research subjects by the NIH Radiation Safety Committee.

There is no direct evidence that the amount of exposure received from participating in this study is harmful. Pregnancy or lactation are exclusionary in this study.

8. Subject Safety Monitoring

8A. Identify monitors during participation in study procedures: In this study the monitors during participation in study procedures are the Principal Investigator, Research Nurse, or Nurse Practitioner.

8.B. Parameters to be monitored: The parameters to be monitored include symptoms and signs. During all study procedures, subjects are monitored by clinically credentialed personnel of the Clinical Neurocardiology Section (Physician, Registered Nurse, or Nurse Practitioner) or authorized personnel of the NIH Clinical Center (e.g., neuroradiologist).

8.C. Toxicity criteria to be used: The Protocol requires monitoring of procedures and possible symptomatic side effects of NAC or the development of a post-spinal headache. The NIH's Common Terminology Criteria for Adverse Events (version 4.0) will be used. The patient is queried about any new symptoms at morning rounds on Day 2 and Day 3 during NAC treatment. If the patient reports gastrointestinal side effects at the initial dose, the dose will be halved. All procedures involving more than minimal anticipated risk are administered only by experienced, qualified personnel or personnel.

8.D. Criteria for stopping individual procedures: The PI has the discretion of stopping individual procedures if the medical or psychological risk outweighs the anticipated scientific benefit.

8.E. Criteria for individual subject withdrawal: If a patient develops a post-spinal headache requiring a blood patch, the subject is withdrawn. Subjects may refuse certain tests or procedures, or may withdraw from participation early, without loss of benefits to which they were previously entitled. The Principal Investigator may also exclude a subject from further participation, such as in the event of known or suspect falsification of medical history information or refusal to undergo planned tests or procedures, without loss of benefits to which the subject was previously entitled. If NAC at the initial dose produces gastrointestinal symptoms, the dose will be halved; and if the gastrointestinal symptoms persist after decreasing the NAC dose, then the patient will be withdrawn from the study. If a patient experiences other symptoms that in the opinion of the Principal Investigator are the result of NAC, the patient may be withdrawn from the study. If a woman becomes pregnant while on study, she will be withdrawn.

8.E.1. Withdrawal definition: For record-keeping purposes, "withdrawal" refers to cessation from any further participation in the study, based on the decision of the participant or the Principal Investigator, before the endpoint for participation has been reached. The endpoint for participation is after obtaining CSF while the patient is on N-acetylcysteine. Reaching the study endpoint for participation does not constitute withdrawal.

9. Outcome Measures

In this study outcome is not related to measures of symptoms or signs or a disease but to CSF neurochemical findings.

9.A. Primary outcome measure

The primary outcome measure is the relative change in CSF Cys-DA levels between pre and post-NAC treatment, which is calculated as: the difference of (CSF Cys-DA at pre-treatment – CSF Cys-DA at post-treatment) divided by CSF Cys-DA at pre-treatment. The change will be dichotomized as decrease vs. no decrease with a threshold decrease to be determined based on the pilot study of HVs.

9.B. Secondary outcome measures

9.B.1. CSF levels of other biochemicals besides Cys-DA. For instance, CSF Cys-DOPA/DOPA ratios may provide an index of oxidative stress in central catecholaminergic neurons.

9.B.2. Percent decrease in CSF Cys-DA expressed as a continuous variable.

9.B.3. In an exploratory study, NAC may be given at 2,000 mg per day.

9.B.4. In a pilot study, reproducibility of CSF Cys-DA will be assessed in a group of HVs studied as inpatients. In this group 2 LPs will be done, separated by 2 days, without NAC treatment prior to either LP. The LPs will be done at about the same time of day, after ingestion of the same pre-determined meal.

10. Statistical Analysis

10.A. Analysis of data/ study outcomes:

For the primary objective, a one-sample t-test (t-test for dependent means) or Wilcoxon signed rank test will be performed to evaluate the difference between pre- and post-NAC treatment for CSF Cys-DA. The proportion of the patients with decreased CSF Cys-DA levels between pre- and post-NAC treatment will be evaluated by the exact binomial test.

For the secondary objectives, one-sample t-tests (t-tests for dependent means) or Wilcoxon signed rank tests will be performed to evaluate the differences between pre- and post-NAC treatment for each secondary outcome.

10.B. Power analysis: Based on the results of the study of HVs, a power analysis will be outlined and approved by the PIRC. The power analysis will be used to justify altering the accrual ceiling for PD patients. The power analysis will be performed using the primary outcome, the difference in CSF Cys-DA between pre- and post-NAC treatment. A one-sample t-test will be applied to estimate the sample size using the standard deviation of the difference calculated from the data in the HVs.

10.C. Accrual ceiling: Based on power analysis, 10-11 patients with complete datasets would be required to achieve the Primary Objective. Considering the possibility of withdrawals, 15 subjects would undergo inpatient testing. In the exploratory study, up to 20 subjects may be needed to test whether NAC at a 2,000 mg per day decreases CSF Cys-DA levels. Therefore, the accrual ceiling for patients in the study as a whole is 35.

The pilot study about biological variability of CSF Cys-DA levels in HVs will include up to 6 HVs with complete datasets. Dropouts will be replaced.

Therefore, the total accrual ceiling under the protocol is $35 + 6 = 41$ participants.

11. Human Subjects Protection

11.A. Subject selection:

11.A.1. Equitability: Participation in this study is offered to eligible subjects, without regard to race, ethnicity, sex, disability, nationality, religion, handedness, age, or English-language ability. Non-English speakers may be included. In this situation, the short-form consent process will be used.

11.B. Justification for exclusion of children: PD is a disease of middle aged or elderly people.

11.C. Justification for exclusion of other vulnerable subjects: This study does not involve pregnant or lactating women, due to the risks involved. Since this research study involves more than minimal risk without direct benefit, those who are unable to provide informed consent are excluded.

11.D. Justification for sensitive procedures: This study does not involve a placebo, medication withdrawal, provocative testing, or deception.

11.E. Safeguards for vulnerable populations:

11.E.1. NIH staff employee protections: NIH staff and members of their immediate families may participate in this NIH intramural research unless prohibited by the NINDS or excluded by the criteria of the study.

Protections for employees and staff participating in this study include 1) assuring that the participation or refusal to participate will have no effect, either beneficial or adverse, on the subject's employment or position at the NIH, 2) giving employees and staff who are interested in participating the "NIH Information Sheet on Employee Research Participation" prior to obtaining consent, and 3) assuring that there will be no direct solicitation of employees or staff. Independent consent monitoring will be provided by the NIH HSPU.

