Study population: The study population comprises up to 35 patients with early (≤ 5 years from diagnosis), mild, levodopa-untreated PD. The patients will be on an inhibitor of monoamine oxidase (MAO) that is prescribed for their disease. There is also a pilot study of healthy volunteers (HVs), to measure biological variability of CSF Cys-DA levels.

Design: The study has a one group, pretest-posttest design. Each patient undergoes a lumbar puncture (LP) as an inpatient at the NIH Clinical Center to obtain cerebrospinal fluid (CSF) for assays of Cys-DA, 3,4-dihydroxyphenylacetic acid (DOPAC), and related biochemicals. The second LP is done after the patient has taken at least 5 doses of NAC (2 grams orally twice per day). The LP takes place about 2 hours after the last NAC dose. For the purpose of establishing biological variance and thereby carrying out a meaningful power analysis, we will study up to 6 HVs who undergo 2 LPs as inpatients, with 48 hours between LPs and no NAC treatment. In the study of HVs the main outcome measure is the biological variation of CSF Cys-DA between the 2 LPs.

Outcome measures: The main outcome measure is the CSF concentration of Cys-DA. Other outcome measures are levels of other catecholamine-related neurochemicals or of indices of oxidative stress. Depending on the results, an exploratory study may be done involving NAC at 1 gram orally twice per day. In the pilot study of HVs the main outcome measure is the biological variation of CSF Cys-DA between the 2 LPs.

Table of Contents:

Précis:	3
List of Abbreviations	5
1. Introduction and Background	6
2. Study Objectives	12
3. Subjects	13
4. Study Design and Methods	14
5. Management of Data and Samples	20
6. Additional Considerations	21
7. Risks and Discomforts	22
8. Subject Safety Monitoring	23
9. Outcome Measures	24
10. Statistical Analysis	25
11. Human Subjects Protection	26
12. Anticipated Benefit	27
13. Classification of Risk (for the study as a whole)	28
14. Consent Documents and Process	29
15. Data and Safety Monitoring	30
16. Quality Assurance	31
17. Reporting of Unanticipated Problems, Adverse Events and Protocol Deviations ..	32
18. Alternatives to Participation	33
19. Privacy	34
20. Confidentiality	35
21. Conflict of Interest	36
22. Technology Transfer	37
23. Research and Travel Compensation	37
24. References	38
25. Attachments/ Appendices	41
26. Consent Forms	42

List of Abbreviations

ALDH = aldehyde dehydrogenase

AR = aldehyde/aldose reductase

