MAO inhibition decreases DOPAL formation. Examination of the concept diagram in Figure 1 leads straightforwardly to the prediction that inhibiting MAO should decrease DOPAL formation, and this is the case (13). There are two isoforms of MAO, MAO-A and MAO-B, and dopaminergic neurons exclusively express MAO-A. At first glance, testing the catecholaldehyde hypothesis would seem to require an MAO-A inhibitor. We wish to avoid using MAO-A inhibitors, because these drugs predispose to paroxysmal

hypertension upon ingestion of common tyramine-containing dietary constituents such as red wine and hard cheese (the “cheese effect”).

MAO-B-inhibitors decrease MAO-A activity in humans. The MAO-B inhibitors selegiline and rasagiline are not associated with the cheese effect (14). These drugs decrease plasma levels of DOPAC and 3,4-dihydroxyphenylglycol, consistent with MAO-A inhibition in sympathetic nerves (13, 15). Selegiline also decreases CSF levels of DOPAC (16), and when administered clinically as a transdermal patch or effervescent tablet, selegiline decreases brain MAO-A activity in humans (17). We have found preliminarily that rasagiline decreases CSF DOPAC (unpublished observations). Therefore, a clinical trial to test the catecholaldehyde hypothesis could be based on MAO-B inhibition.

Treatment with an MAO inhibitor alone might trade off one form of toxicity for another. Large multi-center clinical trials of MAO-B inhibitors have failed to show convincing evidence that this treatment slows the progression of symptomatic PD (18). A variety of explanations have been offered for this failure (19). A relatively recent one is based on our finding that MAO inhibition, while decreasing DOPAL formation, increases spontaneous oxidation of dopamine (13). Treatment with an MAO inhibitor alone might be ineffective because of concurrently decreased enzymatic oxidation and increased spontaneous oxidation of cytoplasmic dopamine.

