Cys-DA in cerebrospinal fluid (CSF) provides a biomarker of spontaneous oxidation of central neural dopamine. Cys-DA is produced from the spontaneous oxidation of cytoplasmic dopamine. We have found that Cys-DA is present in the CSF of healthy humans and patients with PD (23). Our laboratory has the unique capability of simultaneously measuring CSF levels of Cys-DA and of DOPAC. Since DOPAC is produced by the action of MAO on cytoplasmic DA, measuring CSF Cys-DA and DOPAC enables a way to track both spontaneous and enzymatic oxidation of DA. Cys-DA in CSF is probably not derived from released DA, because released DA is highly efficiently metabolized by catechol-O-methyltransferase. Since the vast preponderance of DA production in the brain is in the striatum, most of the Cys-DA in CSF probably reflects a basal ganglia source. Measurement of Cys-DOPA/DOPA is another way to examine oxidative stress in central catecholaminergic neurons.

In this study we will test whether NAC at a dose of 4,000 mg per day decreases CSF Cys-DA levels. The following information is provided as background to justify the chosen dosing regimen of NAC.

NAC is available in different forms and doses. Effervescent and liquid forms of NAC have equivalent plasma bioavailability (24); however, liquid forms have a bad odor and are less well tolerated.

Cetylev™ (500 mg and 2.5 grams), a brand of effervescent, quick-dissolving, flavored tablets, is a trademark of Arbor Pharmaceuticals (Atlanta, GA). Cetylev is FDA approved as an antidote for acetaminophen overdose. Since Cetylev is FDA approved, the company manufactures the drug according to Good Manufacturing Practices (GMP), and Arbor can provide a Certificate of Analysis to verify the identity and potency of the drug. For the clinical indication of acetaminophen overdose, a loading oral dose of 140 mg/kg is given, followed by maintenance doses of 70 mg/kg every 4 hours for a total of 17 doses. Cetylev is available as 500 mg and 2.5 g tablets.

An alternative source is PharmaNAC™ (900 mg), another brand of effervescent, quick-dissolving, flavored tablets. PharmaNAC™ is a trademark of BioAdvantex Pharma (Mississauga, Canada). BioAdvantex Pharma voluntarily complies with essential elements of GMP, from the production of raw materials to the packaging of supplements for distribution. BioAdvantex Pharma has a warehouse in Buffalo, NY.

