Preliminary information: CSF Cys-DA data from 2 patients treated with NAC and 4 HVs who underwent LPs on 2 different occasions under a different protocol are shown in Figure 3. Across the 6 subjects, the correlation coefficient (r value) for the scatter plot relating CSF Cys-DA for the second LP vs. CSF Cys-DA for the first LP was 0.99 (p=0.0002). We predict that in the present study the r value will be even closer to 1 because of the more tightly controlled situation for the 2 LPs. Based on this preliminary information, the reproducibility of CSF Cys-DA is excellent.

[figure not shown]

Figure 3: Scatter plot relating CSF Cys-DA in a second LP to that in a first LP in 2 PD patients (red) and in 4 HVs studied under a different protocol (gray). The linear regression equation for the line of best fit, r value, and p value are shown. Note excellent reproducibility of CSF Cys-DA.

2. Study Objectives

This study is designed to test whether NAC decreases spontaneous oxidation of central neural dopamine in patients with PD.

2.A. Primary objective: The primary objective is to test whether NAC at a dose of 4,000 mg per day decreases CSF Cys-DA levels.

2.B. Secondary objectives: A secondary objective is to evaluate levels of CSF Cys-DA and other catecholamine-related compounds or indices of oxidative stress in CSF or plasma before and after NAC administration. We will also explore whether at a lower dose (2,000 mg per day) NAC produces similar results to those seen with the 4,000 mg per day dose. In a pilot study of HVs we will assess the test-retest variability of CSF Cys-DA.

3. Subjects

3.A. Description of study populations: The study population is patients with PD who are taking an MAO inhibitor for their disease and are not on levodopa. The Planned Enrollment Report for this small study takes into account demographic differences in the prevalence of the disease under study.

The pilot study includes adult HVs.

3.A1. Accrual ceiling: 41.

3.A2. Target number of completers: 10 patients, 6 HVs. Withdrawals/dropouts will be replaced.

3.A3. NIH employees may participate. NIH employees who are subordinates/relatives/co-workers of investigators may not participate.

3.B. Inclusion criteria:

3.B.a. Inclusion criteria for PD Patients

- o PD diagnosed within the past 5 years
- o Taking a monoamine oxidase (MAO) inhibitor
- o Able to provide consent
- o At least 18 years old

3.B.b. Inclusion criteria for Healthy Volunteers

- o Able to provide consent

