4.A.1. Study overview for patients: There is a screening visit and a single inpatient stay. Subjects are studied as inpatients, while on a prescribed MAO inhibitor. Each patient undergoes a lumbar puncture (LP) as an inpatient. A second LP is done after the patient has taken at least 5 doses of NAC over at least 48 hours. The inpatient stay is for up to 8 days. The inpatient stay is less than 8 days if the participant does not develop a post-spinal headache after the second LP. The patient continues his or her MAO inhibitor treatment throughout the hospital stay. The same dose and regimen of MAO inhibitor are used throughout the study in a given patient. This study is not related to other protocols. Subjects are not required to participate in another protocol. There are no follow-up visits under this protocol.

4.A.2. Study overview for HVs: There is a screening visit and an inpatient stay. Each HV undergoes a lumbar puncture (LP) as an inpatient, followed 2 days later by a second LP as an inpatient. While on study, HV subjects are not allowed to participate in another protocol outside the protocols of the Clinical Neurocardiology Section. There are no follow-up visits under this protocol.

4.B. Recruitment: Accruing sufficient patients to meet the Primary Objective within 1 year of initiation of the study will require an effective recruitment plan.

4.B.1. NINDS PD Clinic: The first source of participants will be patients who are in the NINDS PD Clinic database. Personnel of the NINDS PD Clinic will contact

possibly eligible patients to determine whether the patients are interested in participating in the study.

4.B.2. PRPL: The Patient Recruitment and Public Liaison Office (PRPL) will be used for recruitment. The PRPL will distribute recruitment information via the internet to neurology clinics, patient support groups, relevant websites, or other institutions or individuals. A protocol description for lay people is appended (**Appendix 25.C.**). A screening questionnaire is appended (**Appendix 25.D.**). Recruitment strategies to be utilized by the PRPL will include flyers, a Public Service Announcement (PSA), NIH newsletters, ResearchMatch, Clinical Center Facebook, Twitter, CC News/NIH Record, and LISTSERVs. The recruitment flyer is appended (**Appendix 25.K.**).

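### Eligibility sets no stable period on the MAO inhibitor before the first LP, so an effect of that drug still developing between the two LPs would be credited to NAC

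*Combined protocol and SAP*

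**What the plan says.** The inclusion criterion for patients in section 3.B.a is "Taking a monoamine oxidase (MAO) inhibitor". It sets no minimum time on the drug and no stable period before enrolment or the first LP. The eligibility checklist (25.B) is not reproduced, but section 3.D says that it is built from the same criteria.

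Section 4.A.1 covers the study itself: "The patient continues his or her MAO inhibitor treatment throughout the hospital stay", and "The same dose and regimen of MAO inhibitor are used throughout the study in a given patient". Under section 4.C patients are accrued at on-site screening, so the regimen is fixed from screening at the earliest.

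Section 1 says that "MAO inhibition, while decreasing DOPAL formation, increases spontaneous oxidation of dopamine", citing reference 13, and later that "Cys-DA is produced from the spontaneous oxidation of cytoplasmic dopamine".

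On design, the Précis says: "The study has a one group, pretest-posttest design". The only planned test-retest data without NAC come from healthy volunteers: "we will study up to 6 HVs who undergo 2 LPs as inpatients, with 48 hours between LPs and no NAC treatment".

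**The concern.** The background drug that every patient must take is said to act on the pathway that the primary endpoint measures, in the direction opposite to the hoped-for NAC effect. A constant dose is not necessarily a constant effect soon after a start or a change. If Cys-DA is still moving between the LPs for that reason, the movement enters the pre-post difference and nothing in the analysis separates it from NAC.

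The direction depends on the patient. After a recent start or increase, rising Cys-DA would hide a NAC effect. After a recent reduction, falling Cys-DA would imitate one. With a target of 10 completers (section 3.A2; 10 to 11 in section 10.C), one or two such patients could carry weight.

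**Working it through.** **The passages side by side**

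1. *Before screening:* no rule on the MAO inhibitor beyond current use (3.B.a). The exclusion of interfering medication in 3.C.a cannot apply to a drug that inclusion requires.
2. *From screening to the second LP:* regimen fixed (4.A.1). The interval from screening to the first LP is not stated, so this rule narrows the gap by an unknown amount.
3. *Between LPs:* at least 48 hours and at least 5 NAC doses (4.A.1); about 48 hours in 4.D.4. Only movement inside this window matters.
4. *Comparator:* none on an MAO inhibitor without NAC. The healthy-volunteer pilot supplies the responder threshold (9.A) and the SD for power (10.B). It does not select for MAO inhibitor use, so it is not designed to show this drift.
5. *Antioxidants:* section 4.B.8.a requires either a hold of at least 7 days before the first LP, or the same dose and time of day at both LPs. The hold gives the system time to settle; the MAO inhibitor has only the constant-dose half of this rule.

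**How drift enters the outcome**

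Let D = pre − post, so that a positive D is a decrease. With a NAC effect d, a rise g from the MAO inhibitor and error e, D = d − g + e. The paired test in 10.A estimates the mean of d − g. In the relative change of 9.A, the drift enters as g divided by the pre-treatment value.

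**What the sample size implies**

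Section 10.C gives 10 to 11 completers. It cannot be reproduced, because alpha, sidedness, power, effect and SD are not stated. Back-solving a paired t-test at alpha 0.05 gives these standardized effects (mean divided by SD of the difference):

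| Assumption | n = 10 | n = 11 |
|---|---|---|
| two-sided, 80% power | 0.996 | 0.938 |
| two-sided, 90% power | 1.155 | 1.087 |
| one-sided, 80% power | 0.853 | 0.806 |
| one-sided, 90% power | 1.005 | 0.950 |

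For the first cell, the noncentrality is 0.996 × √10 = 3.15, the critical value on 9 degrees of freedom is 2.262, and power is 80%.

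**Illustration, not an estimate for this trial**

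Take n = 10, two-sided 5%, effect 0.996 SD. Let k patients have an upward drift that cancels a fraction of their NAC effect. Simulated power of the paired t-test:

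| Fraction cancelled | k = 1 | k = 2 | k = 3 |
|---|---|---|---|
| 100% | 68% | 55% | 42% |
| 50% | 75% | 70% | 64% |
| 25% | 78% | 76% | 73% |
| 10% | 79% | 78% | 78% |

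In the other direction, with no NAC effect and 1, 2 or 3 of 10 patients drifting down by 1 SD of the difference, a significant decrease appears in about 4%, 6% or 10% of trials, against 2.5% nominal in that tail. The drift sizes and the numbers of patients affected are assumptions; the documents give neither.

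**The case against.** The strongest reply is that the chain from the protocol's statement to drift in a patient's CSF is inferred. Reference 13, which supports the statement that MAO inhibition increases spontaneous dopamine oxidation, is by its title a study in PC12 cells. The documents report no human CSF Cys-DA data around the start or change of an MAO inhibitor. The effect would also have to be still moving within about 48 hours, after an unstated interval since screening. All of this stands. A reader might infer that Cys-DA is in fact drifting, or that the primary result is biased; the documents do not support either.

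A reader might also infer that nothing could reveal a drift. That is too strong. DOPAC is assayed with Cys-DA, section 1 says that MAO-B inhibitors lower it in CSF, and pre-post tests of other CSF biochemicals are planned (9.B.1, 10.A). A shift in DOPAC could hint at changing MAO inhibition. It is only a partial indicator, because NAC might itself alter DOPAC and no drift check is prespecified.

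Nor do the documents say that healthy volunteers take no MAO inhibitor. It is likely, but their listed exclusions do not name it. The safe statement is that the pilot is not designed to show this drift.

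Finally, the power losses depend on the assumed drift: at 10% cancellation they are about 1 to 2 percentage points. The figures show what drift would do if present, not how likely it is.

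What survives is that the criterion leaves the period before screening open, the design cannot separate the two effects, and the protocol already allows for settling before the first LP when a patient stops an antioxidant.

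**Conclusion.** The gap in eligibility is real; the drift is possible, not shown. Patients who began or changed an MAO inhibitor shortly before screening are eligible. Any resulting change in Cys-DA between LPs would be read as a NAC effect or would mask one. Its size, time course and frequency are not in the documents, so no loss of power or excess of false positives can be claimed for this trial. The tabulated figures rest on assumed alpha, power, effect and drift, and should be labelled as such or left out of any summary. Recruiting levodopa-untreated patients within 5 years of diagnosis makes recent starts plausible but does not quantify them. This is an avoidable source of bias with an inexpensive remedy, not a flaw that invalidates the design.

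**What to change.** Amend 3.B.a, and the checklist built from it, to require an unchanged MAO inhibitor regimen for a minimum period before the first LP. The sponsor should set and justify the length from the time each drug takes to reach a steady effect. This would give the MAO inhibitor a settling period comparable in purpose to the antioxidant hold in 4.B.8.a.

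At screening, record the MAO inhibitor's start date and the date of the last dose change. In section 10.A, add a descriptive report of the primary change against time on the current regimen; with about 10 patients this should not be a formal test.

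Nobody's treatment is altered. The cost is one eligibility line, two recorded dates and one descriptive display, plus the deferral of an occasional recently started or changed patient. That deferral matters somewhat, because section 23 calls the eligible subgroup rare and section 4.B aims to accrue within 1 year. If the sponsor judges the restriction too costly, recording the dates and reporting against them is the minimum; it would make the problem visible without preventing it.

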On the day of a LP, the patient may receive a pre-arranged breakfast. The patient receives a pre-arranged lunch in the late morning, to be finished by about 2 hours before the LP. On the day of a LP the patient should have no other oral intake except for medications and water before the LP. When the patient is on NAC, as soon as the lunch is finished, the patient takes 2,000 mg of NAC in water.

At about 2 hours after the pre-arranged lunch meal, a LP for research purposes is done to obtain CSF. For the LP, the subject sits upright (alternatively the subject may be lying sideway with knees curled up toward the chest). The lower back will be cleansed. For local anesthesia, lidocaine without epinephrine will be injected into and through the skin of the back. A needle will be inserted through the anesthetized skin between two lumbar vertebral processes. A total of 6 1-mL aliquots of CSF will be obtained. Each aliquot will be placed immediately on dry ice. It usually takes 5 to 10 minutes to collect the CSF. After the fluid is collected, the needle will be removed.

Flow Diagram (Inpatient Visit): A lumbar puncture (LP) is performed before and after 5 doses of N-acetylcysteine (NAC). The length of the inpatient stay at the NIH Clinical Center will depend on when during the week the patient is admitted and whether the patient has a post-spinal headache. After the second LP, the patient is observed at least overnight (discharge on Day 4). The inpatient visit may last up to 8 days, for insertion of a blood patch and observation in the event of a post-spinal headache after the second LP.

After 5 NAC doses and about 48 hours of NAC administration, the LP for research purposes is repeated. Again, the patient receives a pre-determined lunch at about 12 noon. After the second LP, the subject is observed overnight and is discharged the next day if there is no post-spinal headache.

As noted below, the lumbar puncture may be done under fluoroscopic guidance by a neuroradiologist in the X-ray department.

In HVs, LPs are done also at about 2 hours after ingestion of a pre-determined meal. NAC is not given.

4.D.5. N-Acetylcysteine: In patients, beginning after the first LP, N-acetylcysteine (NAC) is begun at a 2,000 mg by mouth twice daily. HVs do not receive NAC.

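### The fixed 2,000 mg NAC dose before the second lumbar puncture (4.D.4) contradicts the dose-halving rules (7.C, 8.C, 8.E) and is not reconciled with the optional 1 g twice-daily study

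*Combined protocol and SAP*

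**What the plan says.** The operating instructions are in section 4.D.

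- **4.D.4, LP day:** "When the patient is on NAC, as soon as the lunch is finished, the patient takes 2,000 mg of NAC in water". The timing is then set: "At about 2 hours after the pre-arranged lunch meal, a LP for research purposes is done to obtain CSF". The Précis ties the sample to the dose in the same way: "The LP takes place about 2 hours after the last NAC dose".
- **4.D.4, second LP:** "After 5 NAC doses and about 48 hours of NAC administration, the LP for research purposes is repeated".
- **4.D.5, starting dose in patients:** "N-acetylcysteine (NAC) is begun at a 2,000 mg by mouth twice daily".

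Other sections describe two groups whose per-dose amount differs from 2,000 mg.

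- **Patients with gastrointestinal symptoms.** Under 7.C (N-Acetylcysteine), if these occur at the initial dose, "the dose will be decreased by one-half". Sections 8.C and 8.E repeat the halving. Sections 7.C and 8.E then require withdrawal if symptoms occur or persist at the lower dose.
- **An optional lower-dose study.** The Précis says: "Depending on the results, an exploratory study may be done involving NAC at 1 gram orally twice per day". Section 9.B.3 says: "In an exploratory study, NAC may be given at 2,000 mg per day". Section 2.B asks whether the lower daily dose gives results similar to those at 4,000 mg per day, and 10.C allows up to 20 patients for it.

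No visible section states the pre-LP dose for either group, and none gives a separate dosing procedure for the exploratory study.

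**The concern.** The 4.D.4 sentence names an amount and applies to anyone on NAC. For a patient whose dose has been halved, it conflicts with a rule that the protocol states three times. Two things are at stake.

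**Safety instructions.** A symptomatic patient could be given the full amount again just before a research LP. The next step in 7.C also becomes unclear: if symptoms return after a 2,000 mg lunch dose, staff cannot tell whether they arose at the initial or the reduced dose, and withdrawal depends on that.

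**Dose integrity at the outcome sample.** The last dose is the one to which the protocol ties the timing of the CSF sample. If it is the same 2,000 mg in both dose groups, similar results in 2.B could reflect the shared last dose and not the lower daily regimen.

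**Working it through.** **The plan's own figures.** 2 × 2,000 mg = 4,000 mg per day, as in the primary objective (2.A). 2 × 1,000 mg = 2,000 mg per day, as in 2.B, 9.B.3 and 10.C. Accrual also agrees: 15 + 20 = 35 patients (10.C). The daily doses are consistent; the gap concerns the single dose before the LP.

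**Can halving precede the second LP?** Yes, on the protocol's own calendar.

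1. Section 8.C has patients asked about new symptoms on the mornings of Day 2 and Day 3.
2. The flow-diagram text in 4.D.4 has the patient stay overnight after the second LP and leave on Day 4, so that LP falls on Day 3.
3. Lunch on Day 3 follows morning rounds by hours. A patient halved at those rounds therefore meets 7.C, 8.C and 8.E (halved) and 4.D.4 (2,000 mg) on the same day, about 2 hours before the outcome sample.

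**Size for a halved patient.** Assume exactly five doses (4.D.4; the Précis and 4.A.1 say at least five), with the fifth being the lunch dose. Let k be the number of full doses before halving.

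- Halving applied throughout: 2,000k + 1,000(5 − k)
- Halving applied, but 4.D.4 followed for the last dose: 2,000k + 1,000(4 − k) + 2,000

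| k | Halved throughout (mg) | With 4.D.4 (mg) | Excess |
|---|---|---|---|
| 1 | 6,000 | 7,000 | 1,000/6,000 = +17% |
| 2 | 7,000 | 8,000 | 1,000/7,000 = +14% |
| 3 | 8,000 | 9,000 | 1,000/8,000 = +13% |
| 4 | 9,000 | 10,000 | 1,000/9,000 = +11% |

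The excess is always 1,000 mg and lies wholly in the last dose, which is 2,000/1,000 = 2 times the halved amount. A patient halved at Day 3 rounds after four full doses is the row k = 4. There the literal total equals the unreduced regimen, 5 × 2,000 = 10,000 mg, so following 4.D.4 would cancel the halving altogether.

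**Size for an exploratory patient.** Assume the same five-dose schedule, which the documents do not state for this study.

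- 1 g at every dose: 5 × 1,000 = 5,000 mg
- 1 g at four doses, then 4.D.4: 4 × 1,000 + 2,000 = 6,000 mg; 6,000/5,000 = 1.2, or +20%
- Main regimen, for comparison: 10,000 mg

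The last dose is again 2,000 mg instead of 1,000 mg, and so equals the last dose in the main study. The cumulative contrast with the main regimen shrinks from 5,000 mg to 4,000 mg but does not vanish.

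**The case against.** The strongest reply is that 4.D.4 describes the standard LP day, and that a specific, event-triggered reduction rule stated in three places would naturally prevail over a general sentence. Likewise, the exploratory study is defined by its dose, so staff enrolling into it would hardly ignore that dose, and section 4 can be read as the procedures for the main study only. Much of this stands. It shows how a sensible reader might resolve the conflict, but the protocol does not resolve it, and 4.D.4 is the instruction in force at lunch on Day 3.

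Three further points stand in full.

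- Section 4.D.5 gives the dose at which NAC is begun. That is compatible with later halving, so 4.D.5 is not part of the contradiction for halved patients. Its gap is only that it gives no separate starting dose for the exploratory study.
- The exploratory study is conditional, so 20 is a ceiling and not a count of affected patients. The number of patients who would be halved is not given.
- The flow-diagram figures are not shown and the appendices are listed by title only, so the statement that no exception exists covers only the visible text.

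A reader might go further and infer that applying 4.D.5 as well puts exploratory patients on 10,000 mg, with no dose contrast left, or that the exploratory study could say nothing about 2,000 mg per day. The documents do not support this. The first inference requires staff to disregard the dose that defines the study. On the second, a shared last dose with different earlier doses confounds the comparison without making it wholly uninformative.

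**Conclusion.** The concern holds as an internal contradiction. For patients halved before the second LP, 4.D.4 and the rules in 7.C, 8.C and 8.E cannot both be followed, and the protocol's calendar makes the situation possible in the main study whether or not the exploratory study opens. For the optional 1 g twice-daily study, the fixed dose in 4.D.4 is unreconciled with the Précis, 2.B, 9.B.3 and 10.C.

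Read literally, the effect is a doubled last dose in both groups. The excess in total dose is 11% to 17% for a halved patient and 20% for an exploratory patient. These percentages rest on exactly five doses, with the lunch dose as the fifth, and on the exploratory study following the main schedule. The consequence for 2.B is a confounded comparison.

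A reader might also infer that the full dose was meant to be given to these patients, or would be given in practice. The halving rules and the lower-dose objective point the other way, and nothing in the documents establishes either.

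**What to change.** The sponsor should reconcile 4.D.4 with 7.C, 8.C and 8.E, and reconcile 4.D.4 and 4.D.5 with the Précis, 2.B, 9.B.3 and 10.C, so that each patient falls under one dose instruction before the second LP. Which dose or rule applies is for the sponsor to decide; none is proposed here. The milligrams actually taken before the second LP should be recorded for every patient, so that the dose preceding the outcome sample is known at analysis.

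The cost is a wording amendment, mainly to two paragraphs, and one recorded item per patient. No patients or procedures are added.
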